## 11.6. Notification of Serious Breaches to GCP and/or the protocol

A "serious breach" is a breach which is likely to effect to a significant degree –

- a) the safety or physical or mental integrity of the participants of the study; or
- b) the scientific value of the study

The sponsor will be notified immediately of any case where the above definition applies during the study conduct phase

The sponsor will liaise with REC about any serious breach of

- a) the conditions and principles of GCP in connection with the study; or
- b) the protocol relating to that study.

## 11.7. Data protection and patient confidentiality

The CI and study staff will comply with the requirements of the Data Protection Act 2018 and General Data Protection Regulation. or any subsequent amendment or replacement thereof with regard to the collection, storage, processing and disclosure of personal information and will uphold the Directive's core principles.

The CI and study staff will also adhere to the NHS Scotland Code of Practice on Protecting Participant Confidentiality or equivalent.

All study records and data will be managed in a manner designed to maintain participant confidentiality. All records, electronic or paper, will be kept in a secure storage area with access limited to appropriate study staff only. Computers used to collate data will have limited access measures via usernames and passwords.

Personal clinical information will not be released without the written permission of the participant, except as necessary for monitoring or auditing by the Sponsor, its designee or regulatory authorities.

The CI and study staff will not disclose or use for any purpose other than performance of the study, any data, record, or other unpublished, confidential information disclosed to those individuals for the purpose of the study. Prior written agreement from the Sponsor will be required for the disclosure of any said confidential information to other parties.

Access to collated participant data will be restricted to the CI and appropriate delegated study staff. Where data requires to be transferred, an appropriate Data Transfer Agreement will be put in place.

Published results will not contain any personal data that could allow identification of individual participants.

# 11.8. Financial and other competing interests for the Chief Investigator, and committee members for the overall study management

The SMG will aim to identify and disclose any competing interests that might influence study design, conduct, or reporting of results.

## 11.9. Indemnity

The University of Dundee are sponsoring this single centre study.

**Insurance**. – The University of Dundee will obtain and hold Professional Negligence Clinical Trials Insurance cover for legal liabilities arising from the study.

Tayside Health Board will maintain its membership of the Clinical Negligence and Other Risks Insurance Scheme (CNORIS) which covers the legal liability of Tayside in relation to the study.

Where the study involves University of Dundee staff undertaking clinical research on NHS participants, such staff will hold honorary contracts with Tayside Health Board which means they will have cover under Tayside's membership of the CNORIS scheme.

**Indemnity**. The Sponsors do not provide study participants with indemnity in relation to participation in the study but have insurance for legal liability as described above.

#### 11.10. Amendments

The CI will seek Sponsor approval for any amendments to the Protocol or other approved study documents. Amendments to the protocol or other study documents will not be implemented without approval from the Sponsor and subsequent approval from the appropriate REC, as appropriate, and NHS R&D Office(s).

#### 11.11. Post study care

Not applicable

#### 11.12. Access to the final study dataset

The PI and Study Statistician will have access to the final study dataset. Access to the final study dataset to others will be approved by the PI.

#### 12. DISSEMINIATION POLICY

## 12.1. Dissemination policy

There will be a clear PAINSTORM strategy for reporting and dissemination of scientific output, overseen by a dissemination committee. Patient partners will be active members of the dissemination committee. Patient partners will lead the identification of ways of disseminating the results and review outputs aimed at patients and public. Results will be written up in high impact open access scientific papers and presented at scientific conferences internationally. A PAINSTORM website will be created, with public access, and papers will be shared there. Where results potentially affect patient care, e.g. through the identification of stratified approaches to risk management, these will be shared with stakeholders such as patient groups, national regulatory and professional bodies, health professionals and the general public, with a view of maximising overall impact. A Final Report will be prepared for the funding body and for the Ethics Committee.

## 12.2. Authorship eligibility guidelines

The data arising from this study resides with the study team and ownership with the University of Dundee. On completion of the study, the study data will be analysed and tabulated, and a clinical study final report will be prepared. The criteria for authorship will follow the criteria of The International Committee of Medical Journal Editors. The CI will be responsible for authorship of the final report.

## 14. APPENDICIES

# 14.1. Appendix 1 – Schedule of Procedures

	V1 a	V2 a	V3 a	V4 b	V5 b	V6 b	V7 b
					Follow up p	oost chemo	
	Screen & Baseline	Mid Chemo	End of Chemo	3 months	6 months	9 months	12 months
	In cli	inic/ face to	face		Postal/onlin	e/telephone	;
Informed Consent	Х						
ECOG Performance Status Scale	Х	Х	Х				
Disease progression and alterations in oncological treatment plan	х	х	х	х	х	х	х
Eligibility	Х						
Medical History	Х						
Concomitant medications	Х	Х	Х	Х	Х	Х	Х
Lifestyle (inc smoking, alcohol, ilicit drugs)	Х						
Height and weight	Х						
ActivPAL ™ physical activity monitor d	Х	Χ	Х				
Demographics	Х						
NCI CTCAE/AE	Х	Χ	Х				
QST	Х	Х	Х				
Grooved pegboard test	Х	Χ	Х				
MRI scanning	Χ		Χ				
Research Bloods	Х	Χ	Х				
EORTC CIPN 20 ce	Х	Х	Х	Х	Х	Х	Χ
List of body sites/body map ce	Х	Х	Х	Х	Χ	Х	Х
TNSc °	Х	Х	Х				
Chronic Pain Grade ce	Х	Х	Х	Х	Х	Х	Х
BPI ce	Х	Х	Х	Х	Х	Х	Х

DN4 questions e	Х	Х	Х	Х	Х	Х	Х
NeuP Symptom Inventory e	Χ	Х	Х	Х	Х	Х	Χ
	V1 a	V2 a	V3 a	V4 b	V5 b	V6 b	V7 b
EQ-5D-5L21	Χ	Х	Х	Х	Х	Х	Χ
MDASI e	Χ	Х	Х	Х	Х	Χ	Χ
PROMIS	Χ	Х	Х	Х	Χ	Χ	Χ
Pain Catastrophizing Scale	Χ	Х	Х	Х	Х	Χ	Χ
IDS-SR	Χ	Х	Χ	Χ	Χ	Χ	Χ
SOM-7	Χ	Х	X	Χ	Χ	Χ	Χ
TIPI	Χ	Х	Х	Х	Х	Χ	Χ
Saltin-Grimby Physical Activity Level Scale	Χ	X	X	X	X	Х	X

Any of the visits may be carried out over more than one day if participants wish.

<sup>a Visits 1,2 and 3 will not be on the same timescale for all patients as the visits are tailored to the patient's individual chemotherapy schedule.

<sup>b Visits 4-7 will aim to be completed within 1 month either side of scheduled clinical appointments and according to patient preference. There will be no visit windows and it will not be considered a breach of protocol if visits are missed.

<sup>c Participants will fill in pain questionnaires only if they have pain.

<sup>d If participant has opted for an ActivPalTM, they will wear that for the week prior to the cycles of chemotherapy where a face-to-face assessment is planned.

<sup>e Completed remotely (paper/ online/ telephone) prior to each cycle of chemotherapy if no face-to face visit is planned.

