#### 3.3. Primary objective

Use of a deep phenotyping approach to identify psychosocial, clinical and neurobiological factors that are associated with the development and/ or maintenance of painful or non-painful CIPN, as a result of neurotoxic chemotherapy for cancer.

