#### 3.5. Table of Endpoints and outcomes:

**Timepoints:** Face to face assessments at baseline, mid-chemotherapy, end of chemotherapy (timing depends on chemotherapy schedule), with all detailed measures. Note: Blood sampling MRI and use of physical activity monitor are optional (participant preference); MRI will be

offered to 100 eligible participants sequentially. Participants will complete a reduced questionnaire set prior to every cycle of chemotherapy. This can be completed remotely (paper/email/telephone/online) according to participant preference. Pain measures are only completed if pain is present.

Objectives	Outcome Measures	Timepoints measured
Primary		
Development (or persistence) of painless or painful CIPN	EORTC-CIPN20     Change in chemotherapy/dose reduction due to neurotoxicity.	Baseline, mid and end of chemotherapy 3, 6, 9 and 12 months after completion of chemotherapy.
	Pain location: List of body sites / Body map.	Baseline, mid and end of chemotherapy 3, 6, 9 and 12 months after completion of chemotherapy.
	Total Neuropathy Score clinical (TNSc)	Baseline, mid and end of chemotherapy.
Pain severity	
 
Chronic Pain Grade
 
Brief Pain Inventory (BPI) Numeric Rating Scale (average in last 24 hours)
 
	Baseline mid and end of chemotherapy at 3, 6, 9 and 12 months after completion of chemotherapy.
Secondary		
Lifestyle	
 
Eastern Cooperative Oncology Group (ECOG) Performance Status Scale
 
Any changes to planned oncological treatment
 
	
 
Baseline, mid and end of chemotherapy
 
Baseline, mid and end of chemotherapy
 

	Past medical History/ co-morbidities     Family History     Details of cancer type and stage     Oncological treatment including         planned chemo protocol (and any changes to this with reasons)     Duration of CIPN     Smoking questionnaire     Alcohol questionnaire     Illicit drugs	• Baseline
	Concomitant medication	Baseline, mid and end of chemotherapy at 3, 6, 9 and 12 months after

	
 
Physical function: Saltin-Grimby Physical Activity Level Scale
 
Step count (ActivPAL™ accelerometer)
 
Patterns of daily living (time spent sitting,
 
	
 
completion of chemotherapy.
 
Baseline, mid and end of chemotherapy at 3, 6, 9 and 12 months after completion of chemotherapy.
 
Baseline, mid and end of chemotherapy
 

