## Characterisation of pain:

- EORTC-CIPN20
- BPI (including interference subscale).

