#### 8.5. Statistical analysis of clinical data

For the primary analysis, participants will be classified as having a neuropathic or nonneuropathic component, based on their phenotype. Neuropathic phenotypes will be defined as a change of at least 2 on the sensory subscale of the EORTC-CIPN20 questionnaire and/ or dose reduction/ cessation of chemotherapy at any time during the chemotherapy. The primary analysis will be performed on the basis of these two groups. This definition may be modified as PAINSTORM Work package 2 evolves, which focuses on improving assessment to better reflect the experience of people living with NeuP(see 8.7). All continuous variables will be summarised using the following descriptive statistics: n (non-missing sample size), number of missing records, mean, standard deviation, median, maximum and minimum.

The frequency and percentages (based on the non-missing sample size) of observed levels will be reported for all categorical measures.

All summary tables will be structured with a column for NeuP group and an additional column for the total population relevant to that table/treatment, including any missing observations.

The primary analysis will examine the factors which predict the classification into the two groups and aim to establish a prediction model.

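### Appendix 1 makes the EORTC-CIPN20 conditional on having pain, which contradicts its role as the primary measure of painless as well as painful CIPN

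*Protocol*

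**What the plan says.** **Text that ties the CIPN20 to pain (protocol)**

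- Appendix 1 labels the row "EORTC CIPN 20 ce", where the last two letters are footnote markers. Footnote c reads "Participants will fill in pain questionnaires only if they have pain". Footnote e concerns remote completion before cycles that have no face-to-face visit. The row is ticked at all seven visits.
- Section 3.5 gives the same rule in its introduction, "Pain measures are only completed if pain is present", without naming the measures meant.
- Section 7.5 lists the EORTC-CIPN20 first under the heading "Characterisation of pain".

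**Text that needs the CIPN20 from everyone**

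- Section 3.3 sets the primary objective as finding factors associated with the "development and/ or maintenance of painful or non-painful CIPN".
- The table in section 3.5 puts the CIPN20 first among the primary measures, against "Development (or persistence) of painless or painful CIPN".
- Section 8.5 fixes the primary grouping: "Neuropathic phenotypes will be defined as a change of at least 2 on the sensory subscale of the EORTC-CIPN20 questionnaire", and/or "dose reduction/ cessation of chemotherapy at any time during the chemotherapy".

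**The concern.** The instrument that decides the primary classification appears in the schedule under a rule that skips it when there is no pain. Numbness or tingling without pain is part of what the study sets out to explain, and a change score needs a value from before chemotherapy, when many participants may have no pain. If the questionnaire follows the schedule, whether the primary outcome exists for a participant depends on pain. Pain is closely related to that outcome, and baseline pain is also a plausible predictor of it. The prediction model would then be fitted to a sample selected on pain, or to a grouping in which pain-free participants count as non-neuropathic by default unless their chemotherapy was reduced or stopped.

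This is a data-collection rule, so the SAP cannot repair it later. Section 8.3 has the SAP finalised before database lock, by which time the pre-chemotherapy assessments are past. Section 7.5 says the web questionnaire is still to be developed, and section 9.2 bases the data management system on the protocol, so the footnote could become skip logic. Section 8.6 allows multiple imputation only where missing at random is tenable. Under the literal rule no CIPN20 score would be observed in anyone while pain-free, so imputing those scores would be extrapolation.

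**Working it through.** The protocol states no figure on this point that could be reproduced, and n = 200 is given without inputs. The check is mainly a comparison of passages, followed by simple arithmetic.

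**1. Does footnote c reach the CIPN20?** The marker is on its row. Section 7.5 files the form under pain characterisation, and section 3.5 repeats the restriction for pain measures in general. No passage exempts the CIPN20. If it were not meant to be a pain questionnaire, the c on its row would have no function.

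**2. Do the markers look deliberate?** The Chronic Pain Grade, BPI and body-site/body-map rows carry c and e. The DN4 and NeuP Symptom Inventory rows, which are neuropathic pain instruments, carry only e. A neuropathy scale is thus conditional on pain while two pain instruments are not, which suggests misplaced markers.

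**3. What does section 8.5 need?** Change = later sensory score − baseline sensory score. Both terms must exist. Under a literal footnote c, a participant who is pain-free at baseline lacks the second term whatever happens later. A participant with baseline pain who is pain-free at every later assessment lacks the first.

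**4. How many participants would this affect?** Inputs: N = 200 (section 8.1) and p = share with pain before chemotherapy, which the protocol does not give and is assumed here.

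No baseline score = 200 × (1 − p)

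| Assumed p | Baseline score present | No baseline score |
|---|---|---|
| 10% | 200 × 0.10 = 20 | 200 × 0.90 = 180 |
| 25% | 200 × 0.25 = 50 | 200 × 0.75 = 150 |
| 50% | 200 × 0.50 = 100 | 200 × 0.50 = 100 |

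More than half of the baselines are missing whenever p is below 50%. For each p, the middle column is the most participants who could have a change score, because a later score is also required.

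**5. What remains for a participant without a change score?** Of the two limbs in section 8.5, only dose reduction or cessation can still be assessed.

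**6. After correction.** With footnote c off the row, all 200 participants have a scheduled baseline CIPN20, and the change score no longer depends on pain.

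**The case against.** The strongest reply is that this is a labelling slip and not a design decision. Section 3.5 describes the face-to-face visits as including the full set of detailed measures, places the CIPN20 in a different row from pain severity, and links it explicitly to painless CIPN. Section 8.5 takes change scores for granted. Staff may well give the form to everyone. This is fair, and it is why the point is put as a contradiction within the protocol. It does not remove the problem, because the sentence about detailed measures stands in the same introduction as the pain restriction and so does not settle which prevails.

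Four stronger readings are tempting but not supported.

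- *The study could not detect painless CIPN.* A reader might infer this, but NCI-CTCAE, QST and the grooved pegboard test carry no footnote c and are scheduled at V1 to V3, and the dose-reduction limb does not depend on the form. Painless neuropathy would be partly recorded. However, NCI-CTCAE and QST do not enter the section 8.5 classification.
- *The TNSc is certainly under the same rule.* Its marker reads as a degree sign in the text available here. A c is likely, since no such footnote exists, but it needs checking in the source. Section 7.5 lists the TNSc as a clinical examination, which fits poorly with a footnote on questionnaires that participants fill in.
- *Most baselines would be lost.* This needs baseline pain below 50%. The pain exclusion in section 6.2 does not establish that, because it covers only moderate to severe pain from other causes that may confound assessment and cannot be told apart from CIPN.
- *A count of painless cases lost on treatment.* Section 1 gives a CIPN rate of about 67%, or 200 × 0.67 = 134. If 30% to 70% were painless, that is 134 × 0.30 ≈ 40 to 134 × 0.70 ≈ 94. The painless share is assumed, and footnote c does not limit the source of the pain, so a participant with painless CIPN and some other pain would still complete the form. These figures are upper bounds under the assumed shares, not estimates.

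**Conclusion.** The protocol is wrong as written on this point. Its schedule, supported by sections 3.5 and 7.5, makes the CIPN20 conditional on pain, while sections 3.3, 3.5 and 8.5 need it regardless of pain. This rests on the text alone and needs no assumption.

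The size of the loss does rest on assumptions: that the footnote is followed literally, and a baseline pain prevalence the protocol does not state. Over an illustrative 10% to 50%, between 180 and 100 of 200 participants would lack the baseline that the CIPN20 limb needs. The claim is limited to that limb of the primary classification. It is not a claim that painless neuropathy would go wholly unrecorded, nor that the loss will occur if the form is in practice given to everyone. Because a missed pre-chemotherapy score cannot be recovered and the correction is cheap, it should be made before the forms and routing are fixed.

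**What to change.** 1. In Appendix 1, remove footnote c from the EORTC-CIPN20 row. Check the marker on the TNSc row in the source file and remove it there too if it is c.
2. In sections 3.5 and 7.5, state that every participant completes the CIPN20 at every scheduled time point, and has the TNSc at V1 to V3, regardless of pain.
3. In section 7.5, move the CIPN20 out of the pain characterisation list.
4. Replace the general pain-only sentence in section 3.5 with an explicit list of pain-conditional instruments: Chronic Pain Grade, BPI and pain location. Say whether the DN4 and the NeuP Symptom Inventory belong on it.
5. Separate the two uses of the body map. Pain location may depend on pain, but the record of sensory deficits described under clinical examination in section 7.5 should not, since a numb, pain-free participant has deficits to record.

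The cost is wording and questionnaire routing, a few extra minutes of self-completion for pain-free participants, and, if the TNSc was in fact being skipped, that examination at up to three visits that already take place.

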# 14.2. Appendix 2 – Amendment History

Amendment No.	Protocol version no.	Date issued	Author(s) of changes	Details of changes made
